2. NON-SUBSTANTIAL AMENDMENT NO. 1 (04 MAY 2012)

The purpose of this non-substantial amendment (administrative letter) was to notify the Investigators of the following administrative clarifications to Protocol D8350004 (Version 1.0, 02 Mar 2012):

Baseline biomarker samples need only be collected in patients that have met all eligibility criteria and are ready to begin study treatment, thus:

1. Collect one blood sample for each cytotoxic T lymphocyte induction activity (CTL), anti-WT1 antibodies, and retrospective biomarker analyses predose on Day 1 only, and do not collect these samples earlier during screening.
2. The existence of tumor tissue samples for immunohistochemistry (IHC) should be confirmed during the screening period, however, provide these to the sponsor only for patients who receive study drug. Additionally, for patients who require a tumor biopsy at screening in order to provide this tissue sample do not have the biopsy performed until eligibility for the study has been confirmed.

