5. AMENDMENT NO. 3, PROTOCOL VERSION 4.0 (27 MAR 2013)

The following changes were made to the protocol:

- In order to more completely assess disease progression and patient survival, these parameters will continue to be assessed every 3 months following the end of study visit.
- As patients with Grade 2 hematology values may be enrolled in the study and hematologic toxicity has not been observed with WT2725 during this study, the dose-limiting toxicity definition related to hematology parameters has been revised to include at least a 2 grade shift.
- It is not currently known whether administering and evaluating a DTH skin test immediately associated with vaccination or remote from vaccination correlates best with other outcomes. In order to assess and compare both methods, additional DTH skin tests were added at Days 1, 29, and 85, which resulted in adding visits at Days 31 and 87 to evaluate the DTH skin tests. In order to limit the visit schedule burden on patients, Day 2 assessments were moved to Day 3 to coincide with DTH skin test evaluation from Day 1.
- In order to increase the precision of the baseline CTL value upon which changes at subsequent time points are determined, an additional baseline CTL blood sample was included during screening.
- Results of an additional historical tumor assessment prior to baseline, if available, are requested in order to provide more information on tumor progression rate.

- In order to limit testing to patients with a reasonable possibility of a positive result, clarification was provided regarding when hepatitis B and C, human immunodeficiency virus (HIV) 1, and HIV 2 testing are required at screening.
- In order to be consistent with tumor marker response criteria, the window for collection of tumor markers during screening was shortened to 14 days prior to first dose.
- As hematologic toxicity with WT2725 has not been demonstrated in this study, the inclusion criteria for bone marrow and immune reserve was revised by lowering required absolute neutrophil count from $\geq 1500/\mu\text{l}$ to $\geq 1000/\mu\text{l}$, platelets from $\geq 10.0 \times 10^4/\mu\text{l}$ to $\geq 5.0 \times 10^4/\mu\text{l}$ after stem cell transplant, and absolute lymphocyte count (ALC) from $\geq 1000/\mu\text{l}$ to $\geq 500/\mu\text{l}$ after stem cell transplant in order to allow enrollment of a greater and more relevant patient population.

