# 6. EFFICACY AND SAFETY VARIABLES

6.1. Schedule of Assessments

Table 1: Schedule of Assessments for Screening and Vaccine Induction Phase – Part 1

	Screen					Vaccine I	nduction Pl	nase a,b			
	within 14/21 days before	within 7 days before		1st dose		2 nd dose	3 rd dose	4 th dose		5 th dose	
	1 st dose (-1 – -14/-21)	1 st dose (-17)	Day	Day 1 (-	Day 3	Day 8 (-	Day 15 (-1)	Day 22 (-1)	Day 27	Day 29 (-1)	Day 31
Informed consent	X										
Inclusion/exclusion	X	X									
Continuation criteria				X c		X c	X c	X c		X c	
Study drug administration				X		X	X	X		X	
Medical history	X										
Physical exam		X		X c		X c	X c	X c		X c	
Height		X									
Weight		X		X c		X c	X c	X c		X c	
Vital Signs d		X		X c		X c	X c	X c		X c	
ECOG performance status		X		X c		X c	X c	X c		X c	
HLA typing e	X										
Serum pregnancy test f	X			X c							
Serology g	X										
Hematology/ serum chemistry h		X		$X^{c,i}$		X c	X c	X c		X c	
Urinalysis		X		$X^{c,i}$			X c			X c	
12-lead ECG		X		X c,i						X c	
DTH skin test injection			X j	$X^{j,k}$					$X^{j}$	$X^{j,k}$	

Table 1: Schedule of Assessments for Screening and Vaccine Induction Phase – Part 1 (Continued)

		ening					Induction Phase a,t				
	within	within 7		1 st dose		2 nd dose	3 rd dose	4 th dose		5 th dose	
	14/21 days before 1 st dose (-1 – -14/-21)	days before 1 st dose (-17)	Day -2	Day 1 (-1)	Day 3	Day 8 (-1)	Day 15 (-1)	Day 22 (-1)	Day 27	Day 29 (- 1)	Day 31
DTH skin test evaluation 				X m	X n					X m	X n
Blood sample for CTL		X		X c		X c	X c	X c		X c	
Blood sample for Anti-WT1 antibody				X c			X c			X c	
Blood sample for PBMC isolation				X c						X c	
Blood sample for retrospective biomarker analyses				X c,o	Xº	Xc	X c			X°	

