# 8. STATISTICAL ANALYSIS

In this section and all after, when tables are presented by posttreatment visits, the last visit will be the visit at the end of study. When applicable, visits after the start of the maintenance phase and unscheduled visits will be included in a summary of maximum and minimum values observed for each patient's posttreatment visits, i.e., the minimum and maximum values are based on all the post treatment visits.

In general descriptive statistics for continuous variables will be summarized by the mean, standard deviation, 25th percentile, median (50th percentile), 75th percentile, minimum and maximum values. When continuous variables are displayed for less than 3 patients, only the number of observations will be presented. Categorical variables will be summarized using counts and percentages.

All raw data will be presented to the original number of decimal places. The means and medians will be presented to 1 more decimal place than the raw data. The standard deviations will be presented to 2 more decimal places than the raw data.

Baseline will generally be defined as data obtained as the last non-missing value prior to the first dose of study drug, i.e., including the pre-dose assessment on Day 1, assessments during screening and other assessments prior to the first dose of study drug.

AE tables and laboratory tables will be presented by visits and by tumor group. Tumor groups are defined as groups of overall, solid tumor, and AML patients.

Unless otherwise stated, summaries will be produced by dose cohort, which is defined as the intended and starting dose to which the patient was enrolled.

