## 8.3. Analysis Populations

There are 3 planned analysis populations.

- Safety population: includes all enrolled patients who receive at least 1 dose of study drug and will be used for the analysis of all safety and efficacy data except as noted below
- DLT population: includes all patients in the Safety population who experience a DLT within the DLT evaluation period or completed the DLT evaluation without experiencing a DLT and will be used for analysis of DLT.
- Efficacy population: include all patients in the Safety population who are evaluable for response (for each irRC, IWG, CA-125 and WT1 by RT-PCR)
  - o Population for irRC response: including all the patients in the Safety population who are not AML patients and whose lesions are measureable and have at least one posttreatment assessment. (Note that any posttreatment irRC assessment is based on the baseline assessment)
  - O Population for modified IWG response: includes all the AML patients in the Safety population who have >5% marrow blasts or >50 copy/μ g RNA of quantitative RT-PCR for WT1 transcript before the first date/time of study drug and who have at least one posttreatment assessment.
  - o Population for CA-125 tumor marker: including all ovarian cancer patients in the Safety population who have a baseline CA-125 assessment and at least one assessment posttreatment.
  - Population for WT1 by RT-PCR tumor marker: includes AML patients in the Safety population who have a baseline assessment and at least one assessment posttreatment.
- Population for CTL: including all patients in the Safety population who has a baseline assessment of percentages of WT1-positive cells among CD8-positive cells and at least one post-baseline assessment

Additional populations for analyses of other tumor markers identified may be defined in a similar manner.

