#### 8.6.3.1. CTL Evaluation

A patient is considered a CTL responder if s/he has:

• Two or more post-baseline visits (no need to be consecutive) with >=2-fold increase from baseline, if the baseline is not 0,

Or

 Only one post-baseline visit with >=2-fold increase from baseline when the total number of post-baseline visits is <=4, if the baseline value is not 0,

 Or

• At least one post-baseline value > 0, if a patient has baseline of 0

A table will present the number and percentage of patients for their CTL response. Additionally, geometric mean, geometric SD, the mean, standard error (se), SD, median, 25 and 75 percentile of baseline assessments and the corresponding same descriptive statistics for both mean of post-baseline assessments for each patient and maximum of post-baseline assessments for each patient will be presented by dose cohort and overall, where geometric mean is

$$\mu_{\mathbf{g}} = \sqrt[n]{A_1 A_2 \cdots A_n}.$$

and geometric SD is

$$\sigma_g = \exp \sqrt{rac{\sum_{i=1}^n (\ln rac{A_i}{\mu_g})^2}{n}}.$$

The Wilcoxon singed-rank test will be performed to see the difference between the baseline assessments and the mean of post-baseline assessments for each cohort and overall as well as the difference between the baseline assessments and the maximum of post-baseline assessments for each cohort and overall. Bar plot of mean and SE of baseline and mean of post-baseline assessments will be presented as well as baseline vs. maximum of post-baseline assessments stratified by both dose cohorts and cancer types. Similar bar plots are generated for the median and quartiles.

The percent change from baseline will be presented over time graphically. A by-patient listing will be provided.

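### The screening CTL draw was added to make the CTL baseline more precise, but the SAP's last-value rule leaves it out of that baseline whenever a Day 1 value exists

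*SAP*

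**What the plan says.** **Purpose of the extra draw.** The administrative letter of 04 May 2012 limited CTL sampling to "predose on Day 1 only, and do not collect these samples earlier during screening". Protocol Amendment 3 (27 Mar 2013) changed this by placing one further CTL sample in the screening period. Its stated reason was: "In order to increase the precision of the baseline CTL value upon which changes at subsequent time points are determined".

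**Current schedule.** In SAP Section 6.1, Tables 1 and 3, the row "Blood sample for CTL" is marked within 7 days before the first dose and again predose on Day 1. Each part therefore has two pre-dose draws, followed by one at every dosing visit.

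**Baseline rule.** SAP Section 8: "Baseline will generally be defined as data obtained as the last non-missing value prior to the first dose of study drug". Section 8.6.2 sets a separate baseline for tumor assessments. No separate one is set for CTL.

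**Use of the baseline.** The CTL population (Section 8.3) takes any patient who "has a baseline assessment of percentages of WT1-positive cells among CD8-positive cells and at least one post-baseline assessment". Section 8.6.3.1 calls a patient a responder on "Two or more post-baseline visits (no need to be consecutive) with >=2-fold increase from baseline, if the baseline is not 0". One such visit is enough when there are four or fewer post-baseline visits, and any positive later value is enough when the baseline is 0. The same section compares baseline with the mean and the maximum post-baseline value by signed-rank test, and plots percent change.

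**The concern.** The design pays for a second pre-dose sample and gives the reason, but the analysis rule does not use it for that purpose. The baseline is the reference for every later visit of the same patient, so its error is shared across visits and longer follow-up cannot average it out. A chance-low Day 1 value can produce repeated 2-fold rises with no vaccine effect; a chance-high one can hide real rises. A single chance zero is worse, because any later positive value then makes the patient a responder.

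CTL induction is a secondary endpoint variable (SAP Section 6.3). What is at stake is the reliability of the CTL responder rate and of the change from baseline by dose cohort.

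**Working it through.** The plan gives no CTL variance, effect size or precision target (Section 4.3 ties sample size to the dose cohorts), so there is no planned figure to reproduce.

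**Inputs**
- Pre-dose draws: 2 (Tables 1 and 3).
- Post-baseline draws: 8, for Part 1 doses 2 to 9. As 8 exceeds 4, the two-or-more-visits rule applies.
- Within-patient CV: not in the documents. Assumed 30%, 50% and 70%, log-normal, with σ = √ln(1+CV²) = 0.294, 0.472 and 0.631.
- Draws independent, with no true change.

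**Step 1. Which value becomes baseline.** The last non-missing value before dosing is the predose Day 1 draw whenever that is available. The screening draw becomes baseline only if Day 1 is missing.

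**Step 2. Variance on the log scale** (s² = variance of one log draw)
- Single-visit change: s² + s² = 2s² with one draw; s² + s²/2 = 1.5s² with the mean of two log draws. The ratio is 0.75: 25% less variance, and 13% less SD (√0.75 = 0.866).
- Mean of eight visits against baseline, approximately: s²(1 + 1/8) = 1.125s² against s²(1/2 + 1/8) = 0.625s². The SD ratio is √(0.625/1.125) = 0.745, about 25% less. Simulation with the arithmetic mean gives 23–25% across the three CVs.
- With one draw, the baseline supplies 1/1.125 = 89% of the variance of that second measure.

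**Step 3. False responders, no true change, eight visits** (simulated)

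| Assumed CV | Last draw | Arithmetic mean of two | Geometric mean of two |
|---|---|---|---|
| 30% | 8.8% | 3.5% | 4.0% |
| 50% | 28.9% | 20.1% | 23.6% |
| 70% | 41.1% | 32.8% | 38.6% |

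**Step 4. How much of this is precision.** The arithmetic mean of two log-normal draws also lies above the typical single draw, which makes a 2-fold rise harder to reach. Taking the geometric mean as the pure precision effect, the share of the drop due to this upward shift is:
- CV 30%: (4.0 − 3.5)/(8.8 − 3.5) = 9%
- CV 50%: (23.6 − 20.1)/(28.9 − 20.1) = 40%
- CV 70%: (38.6 − 32.8)/(41.1 − 32.8) = 70%

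At an assumed CV of 100% the geometric mean gives no gain (four visits: 56.1% with the last draw, 57.4% with the geometric mean; nine visits: 53.4% and 54.4%).

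**Step 5. Zero baselines.** If a draw reads 0 by chance with probability p, a one-draw baseline is 0 with probability p, and both of two draws are 0 with probability p². For p = 10%, 20% and 30% that is 10%, 20% and 30% against 1%, 4% and 9%.

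**Step 6. Sensitivity to independence.** If the errors of the two pre-dose draws correlate at ρ, and not with later draws, the single-change variance becomes s²[1 + (1+ρ)/2]. At ρ = 0.5 that is 1.75s², a reduction of 12.5% instead of 25%.

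**The case against.** **The draw is not thrown away.** A reader might infer that the SAP discards it. The documents do not support that. The Section 8 rule is hedged as general, the screening value stands in when Day 1 is missing, Section 8.6.3 allows tables of the screening assessment, and Section 8.6.3.1 provides a by-patient listing. The draw is left out of the baseline only, but that was its stated purpose.

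**The amendment does not say to average.** True. It states a purpose, not an estimator, and the protocol text to hand is an amendment history. The mean is a statistical inference from the purpose. The Amendment 3 wording is used here only for intent; the current SAP schedules confirm that both draws remain.

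**Averaging makes precision differ by cohort.** This is the strongest objection, and it stands. Before 27 Mar 2013 the rule was Day 1 only, and Amendment 4 (31 May 2013) already reports an identified RP2D. Lower-dose cohorts therefore probably have mostly one draw and later cohorts two, though the split is not stated. With no effect at all, the responder rate could be 8.8% in one-draw and 3.5% in two-draw cohorts at CV 30%, or 28.9% and 20.1% at CV 50%: an artificial dose difference. A uniform last-value rule avoids this, so it is needed as a sensitivity analysis.

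**The gain might cost sensitivity.** Mostly not. With a true 2.5-fold rise, detection goes from 92.6% to 96.3% (CV 30%) and from 88.3% to 91.7% (CV 50%) with the arithmetic mean. With a true 1.5-fold rise it falls from 45.4% to 40.7% (CV 30%), but that rise is below the plan's own threshold.

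**Skin-test exposure.** A reader might also infer that the Day −2 skin test with WT2725 peptide distorts the Day 1 value and that the screening draw is clean. The screening window runs to Day −1, so that draw can follow the test too, and no document says the test shifts CTL within two days.

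**Conclusion.** The point holds as a mismatch between the reason for the screening CTL draw and the baseline rule that reaches it. When Day 1 is present, the added draw affects no baseline-referenced CTL result.

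The 25% variance reduction for a single log change needs only equal variance, independent errors and averaging on the log scale. The false-responder figures rest further on assumed CVs, log-normal draws and eight visits. They show direction and plausible range, not what this trial would observe, and at higher CVs much of the arithmetic-mean benefit is a shift in baseline rather than precision.

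The change is worth making but is not critical. CTL is a secondary variable analysed descriptively with unpowered tests, and no dose or stopping decision depends on it. The primary DLT/MTD analysis is unaffected.

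**What to change.** Add to SAP Section 8.6.3.1, before CTL results are examined:

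- CTL baseline is the arithmetic mean of all values obtained before the first dose (screening and predose Day 1). If only one exists, that value is used.
- The zero-baseline responder rule applies only when every pre-dose value is 0. One zero and one positive draw give a positive baseline. A geometric mean would turn that case into a zero baseline, which is one reason to name the arithmetic mean explicitly.
- This baseline is used for the responder definition, percent change, descriptive tables and signed-rank tests. All other parameters keep their present baseline rules.
- The CTL responder and change analyses are repeated with the last-value baseline as a sensitivity analysis. The number of patients with one and with two pre-dose draws is shown for each dose cohort, and any cohort difference that appears under only one definition is not read as a dose effect.

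Cost: a few SAP sentences, one derived variable and one extra set of CTL tables. Both samples are already scheduled. The remaining downside is unequal baseline precision between early and later cohorts, which the sensitivity analysis exposes but does not remove.

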# 8.1. Disposition of Patients

The number and percentage of patients will be presented by dose cohort, together, with the number and percentage of patients who withdrew from the study for each study discontinuation reason.

A tabulation of the number and percentage of patients treated at each center will be presented. Additionally, a summary of the number of patients starting each dose within each treatment phase will be presented.

A listing of all patients discontinued from the study will be presented by dose cohort including a patient identifier, treatment center, the specific reason for discontinuation, and the duration of treatment before discontinuation.

## 8.2. Important Protocol Deviations

Important Protocol Deviations (IPD) will be identified and documented based on a review of potentially IPDs. Potential Important Protocol

Deviations will be defined as those collected with a significance of "major". The potential IPDs will be identified through programmatic checks of study data, as well as through review of selected data listings. Potential IPDs will be assessed as to whether or not they have a significant impact on the assessment of safety or efficacy. The IPD categories include, but are not limited to:

- Did not meet inclusion/exclusion criteria
- Did not meet continuation criteria
- Received any disallowed concomitant medication and therapy

Per PRA processes, IPD data will be entered into PRA's Clinical Trials Management System (CTMS). The study team and the sponsor will conduct ongoing reviews of the IPD data from CTMS and the resulting set of evaluable patients throughout the study, adjusting the IPD criteria as appropriate. The evaluable patients set should be finalized at the post-freeze data review meeting (or earlier), prior to database lock.

Specific IPDs, category codes and deviation codes are outlined in the Protocol Deviation Guidance document as noted in the Clinical Management Plan.

The number of patients with each type of IPD will be tabulated by deviation category and by deviation type for all patients in the Safety population by dose cohort. A listing of all deviations including deviation date, deviation type, significance (major vs minor), deviation description and any relevant comments will be generated.

## 8.3. Analysis Populations

There are 3 planned analysis populations.

- Safety population: includes all enrolled patients who receive at least 1 dose of study drug and will be used for the analysis of all safety and efficacy data except as noted below
- DLT population: includes all patients in the Safety population who experience a DLT within the DLT evaluation period or completed the DLT evaluation without experiencing a DLT and will be used for analysis of DLT.
- Efficacy population: include all patients in the Safety population who are evaluable for response (for each irRC, IWG, CA-125 and WT1 by RT-PCR)
  - o Population for irRC response: including all the patients in the Safety population who are not AML patients and whose lesions are measureable and have at least one posttreatment assessment. (Note that any posttreatment irRC assessment is based on the baseline assessment)
  - O Population for modified IWG response: includes all the AML patients in the Safety population who have >5% marrow blasts or >50 copy/μ g RNA of quantitative RT-PCR for WT1 transcript before the first date/time of study drug and who have at least one posttreatment assessment.
  - o Population for CA-125 tumor marker: including all ovarian cancer patients in the Safety population who have a baseline CA-125 assessment and at least one assessment posttreatment.
  - Population for WT1 by RT-PCR tumor marker: includes AML patients in the Safety population who have a baseline assessment and at least one assessment posttreatment.
- Population for CTL: including all patients in the Safety population who has a baseline assessment of percentages of WT1-positive cells among CD8-positive cells and at least one post-baseline assessment

Additional populations for analyses of other tumor markers identified may be defined in a similar manner.

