#### 4. STUDY DESIGN

# 4.1. General Description

This is a Phase 1, open-label, dose-escalation, 2-part study in adult patients with advanced malignancies known to overexpress the WT1 protein. The study will primarily evaluate DLT and define the MTD of WT2725 Dosing Emulsion during the DLT Evaluation Period, which extends from the day of the first dose of study drug to just prior to the fifth dose (Days 1 - 29). In addition, antitumor activity and biomarkers indicative of immune response will be evaluated from the first dose until discontinuation of the patient from the study. An end of study assessment will take place within 28 days after the last dose of study drug and prior to the start of alternate antineoplastic therapy.

The initial patients in each dose escalation cohort will be enrolled at least one week apart to evaluate initial safety from the first 2 patients, then a "rolling-six" design will be employed that allows accrual of 2 to 6 patients concurrently in each dose escalation cohort.

In Part 1 of the study, the 0.3 mg cohort will be conducted first. After safety and tolerability have been established for the first cohort, enrollment of subsequent patients will be conducted sequentially in subsequent cohorts and continue until the MTD or all planned cohorts are attained. Enrollment of each cohort may include patients with any of the eligible tumor types (see below). Enrollment of the highest tolerable dose cohort (MTD or highest planned cohort) will continue until there are at least 6 patients total in the study with each tumor type that are evaluable for DLT, biomarkers, and response. This dose is considered the recommended phase 2 dose (RP2D). Enrollment of up to 3 RP2D cohorts of 10 patients each of a specific tumor type may take place at this dose in order to further characterize the safety and efficacy of WT2725 Dosing Emulsion at this

dose in these subsets of patients. Additional dose escalation cohorts after the initial expansion cohorts may be enrolled if a MTD has not been determined and significant signs of toxicity have not been observed in the expansion cohorts.

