- Tumor assessments (per irRC for solid tumors, modified IWG for AML, and/or standard tumor markers as appropriate eg, CA-125 for ovarian carcinoma and quantitative RT-PCR for WT1 transcript for AML) are not required to be repeated if they have been performed within the 28 days before first dose (there are no variations allowed beyond this window). If multiple assessments are available, the most recent ones should be used as the baseline result. Data from at least one additional historical assessment prior to the baseline assessment should also be provided, if available. Progressive disease requires confirmation by a repeat, consecutive assessment at least 4 weeks after the date of first documentation, unless rapid clinical deterioration is seen. For patients with glioblastoma, progressive disease should additionally be confirmed by SPECT, perfusion MRI, MRI spectroscopy or C-14 methionine PET or pathology from available surgical/biopsy specimens to differentiate from pseudoprogression. For patients with ovarian cancer that express CA-125, progressive disease should additionally be confirmed by CA-125 (≥ 2x higher of ULN or on study nadir). For patients with AML, bone marrow aspirations/biopsies are to be provided at baseline and subsequently when clinically indicated, however peripheral blood should be assessed for blasts and WT1 transcript at baseline and at least every 4 weeks or more frequently as clinically indicated.

Table 2: Schedule of Assessments for Consolidation Phase, Maintenance Phase, and End of Study – Part 1

	Consolidat	tion Phase a,b					Maintenanc e Phase a,b	End of Study	, b	Follow-up
	6 th dose	7 th dose	8 th dose		9 th dose					
	Day 43 (±2)	Day 57 (±2)	Day 71 (±2)	Day 83	Day 85 (±2)	Day 87	every 28 (+7) days	48 hours before End of Study Visit	within 28 days after last dose	every 3 months
Continuation criteria	X c	X c	X c		X c		X c			
Study drug administration	X	X	X		X		X			
Physical exam	X c	X c	X c		X c		X c		X	
Weight	X c	X c	X c		X c		X c		X	
Vital Signs d	X c	X c	X c		X c		X c		X	
ECOG performance status	X c	X c	X c		X c		X c		X	
Serum pregnancy test e									X	

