## 8.6.2. Secondary Analyses

The number and percentage of patients will be presented according to categories of irRC, IWG, and /or tumor markers of CA-125 and WT1 by RT-PCR by dose cohort displaying their best response on-study.

The baseline assessment for patients with solid tumors or AML is defined as the assessment at screening, obtained within the 28 days prior to the planned first dose of the study drug. If multiple assessments are available, the most recent one should be used.

Tumor assessments will be conducted during screening, and then every 8 weeks after the first dose of study drug. All tumor assessments may be performed within  $\pm 7$  days of the scheduled assessment but must be completed before study drug is administered. All patients should complete an End of Study visit within 28 days after the last dose of study drug and prior to the start of alternate antineoplastic therapy.

A listing of patients with nonenhancing lesion assessments will be provided.

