#### 8.6.2.3. Tumor Markers

CA-125 and WT1 by RT-PCR will be summarized for only ovarian cancer and AML patients, respectively. Additional tumor markers may be identified and summarized as appropriate.

To evaluate the response according to CA-125, the definition of response described in Rustin, et al. [Rustin-2011] will be used. A response according to CA-125 has occurred if there is at least a 50% reduction in CA-125 levels from baseline sample. This response must be confirmed at least 28 days later by a repeat assessment that is a at least a 50% reduction or is within 10% ( $\pm$  10%) using the same assay method. Additionally, the baseline must be at least 2 times the upper limit of normal and drawn within 4 weeks prior to first dose date. Progression is defined as an increase of 2 times the nadir value at any time. If the nadir is less than the upper limit of normal then a progression will be declared at 2 times the upper limit of normal. This must be confirmed at least one week

later. Not-response/Non-PD will be assessed if neither the criteria of response or progression are achieved. A table will present the number and percentage of patients for their best response (response>Not-response/Non-PD>progression) for the CA-125 population. Additionally, the percent change from baseline may be presented over time graphically.

The descriptive statistics for the log transformed RT-PCR value will be presented for bone marrow and blood separately by each assessment and by different cohort. For any assessment, if there are multiple assessments within each category (either bone marrow or blood), choose the highest one. If the result of RT-PCR is undetectable, impute it as half of  $5.0 \times 10 \text{ copy}/\mu g$  RNA. The percent change from baseline will be presented over time graphically for WT1 by RT-PCR for the log transformed RT-PCT values.

Additionally, other markers identified upon review may be summarized and/or categorized according to standard criteria.

A by-patient listing for both CA-125, WT1 by RT-PCR, and other tumor markers identified will be provided separately.

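### The CA-125 response percentage counts in its denominator patients whose baseline is below twice the upper limit of normal, who cannot respond under the SAP's own rule.

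*SAP*

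**What the plan says.** The set and the response rule stand in different SAP sections.

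- **Set (8.3).** The CA-125 population is described as "including all ovarian cancer patients in the Safety population who have a baseline CA-125 assessment and at least one assessment posttreatment". No CA-125 level is required at baseline.
- **Response rule (8.6.2.3).** A response is a fall of at least half from baseline, confirmed by a repeat sample at least 28 days later. The rule then adds: "Additionally, the baseline must be at least 2 times the upper limit of normal and drawn within 4 weeks prior to first dose date".
- **Everyone else (8.6.2.3).** "Not-response/Non-PD will be assessed if neither the criteria of response or progression are achieved".
- **Table (8.6.2.3).** "A table will present the number and percentage of patients for their best response (response>Not-response/Non-PD>progression) for the CA-125 population".
- **Baseline window (8.6.2).** For solid tumors and AML the baseline "is defined as the assessment at screening, obtained within the 28 days prior to the planned first dose of the study drug".

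Section 8.6.2 presents these categories by dose cohort.

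**The concern.** The floor is part of the definition of response but not of the definition of who is counted. Take a patient who starts below 2 x ULN and whose CA-125 halves, with confirmation. By rule that patient is not a responder. The classification is Not-response/Non-PD, or progression if that criterion is met, and the patient stays in the denominator of the response percentage.

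Such a patient says nothing about whether the treatment produces CA-125 responses, because the outcome was fixed before the first dose. A reader of the table would take the percentage as a response rate. It would in fact mix that rate with the share of patients who entered with a high enough CA-125. Antitumor response, including response by tumor markers, is a stated secondary objective (SAP 3.2).

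**Working it through.** **Inputs from the documents.** The set and the rule are as quoted above. The SAP gives no expected CA-125 response rate and no planned number of ovarian patients with raised CA-125, so there is no planned figure to reproduce. For scale, section 4.1 continues enrollment at the highest tolerable dose "until there are at least 6 patients total in the study with each tumor type that are evaluable for DLT, biomarkers, and response", which gives a per-type minimum of 6. It also allows up to 3 single-tumor cohorts of 10 at the recommended phase 2 dose, but does not say that any of them is ovarian.

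**Assumed inputs.** The number who qualify (q) and the number of responders (r) are not in the documents. Both are assumed below.

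**Formulas.** Let N be the size of the CA-125 population, q the number with baseline at least 2 x ULN, and r the number of responders (r cannot exceed q).

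- Reported percentage = r / N
- Rate among assessed patients able to respond = r / q
- Ceiling on the reported percentage = q / N
- Hence reported = (r / q) x (q / N)

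**Results.**

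| N | r | q | Reported r/N | Able to respond r/q | Ceiling q/N |
|---|---|---|---|---|---|
| 6 | 2 | 6 | 33% | 33% | 100% |
| 6 | 2 | 5 | 33% | 40% | 83% |
| 6 | 2 | 4 | 33% | 50% | 67% |
| 6 | 2 | 3 | 33% | 67% | 50% |
| 10 | 3 | 10 | 30% | 30% | 100% |
| 10 | 3 | 8 | 30% | 38% | 80% |
| 10 | 3 | 6 | 30% | 50% | 60% |
| 10 | 3 | 4 | 30% | 75% | 40% |

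Check for N = 6, q = 4: 50% x 67% = 33%, the reported figure.

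If q = N, or if r = 0 with at least one patient qualifying, the two rates agree and nothing is understated.

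**The 4-week condition is not a second gap.** The response rule also asks for a baseline drawn within 4 weeks of first dose, but 8.6.2 and the Table 1 footnote on tumor assessments already set a 28-day window.

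**Can such patients occur?** The Table 1 footnote says "For patients with ovarian cancer that express CA-125, progressive disease should additionally be confirmed by CA-125". By limiting that rule to patients who express the marker, the plan allows for ovarian patients who do not. It gives no count.

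**The case against.** **One table, one denominator.** The table has three mutually exclusive categories, and progression needs no 2 x ULN baseline. A single set is coherent for the table as a whole. This stands, and it is why the full population should be kept for progression. It does not make the response line interpretable.

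**The floor may be implied.** The parent line in 8.3 limits the Efficacy population to patients evaluable under each criterion. But the CA-125 line beneath it is the working definition and omits the floor, whereas the irRC and IWG lines in the same list do state baseline disease conditions. If the floor was meant, it should be written.

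**The by-patient listing shows the values.** It lets a reader find the affected patients, but it does not correct the tabulated percentage.

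**The illustration is loosely anchored.** This is fair. Six is a whole-study minimum per tumor type, described as evaluable for response, while the table is by dose cohort. The splits are invented and show only how the arithmetic behaves.

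**A stronger reading: the CA-125 rate is biased low overall.** A reader might infer this, but the documents do not support it. The same set drops ovarian patients with no posttreatment CA-125, which can push the rate up. Suppose 6 patients are assessed, 1 of them below the floor, with 2 responders, and 2 further qualifying patients have no posttreatment sample. The reported rate is 2/6 = 33%. Against all qualifying treated patients it is 2/(5 + 2) = 29%. The net direction is unknown.

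**Another stronger reading: the irRC and IWG rates are inflated by leaving out unassessed patients.** The set definitions do require a posttreatment assessment; the irRC set covers patients "who are not AML patients and whose lesions are measureable and have at least one posttreatment assessment". But the table descriptions in 8.6.2.1 and 8.6.2.2 name no population. The first has an unevaluable class for patients with no post-baseline evaluation, and the second ranks a Missing category. The author may have meant to show those patients. What can be supported is a mismatch to clear up, not a demonstrated exclusion.

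**Conclusion.** The point holds in a limited form. As written, assessed ovarian patients below 2 x ULN at baseline cannot be CA-125 responders but are counted in the CA-125 response denominator. The reported percentage is capped at the share who qualify. It is below the rate among assessed patients able to respond whenever there is at least one responder and at least one patient below the floor.

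The cap and the direction of that comparison follow from the SAP text alone. The size does not, because the number below the floor is not given: at 2 responders of 6 the gap runs from nothing (all 6 qualify) to 33% against 67% (3 qualify). No claim is made about bias relative to all treated ovarian patients.

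The endpoint is secondary and descriptive, and the SAP attaches no test or decision rule to it. DLT and MTD are unaffected. Only the amendment summaries of the protocol are available, so this rests on the SAP and the protocol's own statistical section could not be compared. The change is worth making because it is cheap and removes a misleading percentage.

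**What to change.** In SAP 8.3 and 8.6.2.3:

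1. Compute the CA-125 response percentage among patients in the CA-125 population whose baseline, within the 28-day window, is at least 2 x ULN. Count those without a confirming sample as non-responders.
2. Keep the full CA-125 population as the denominator for CA-125 progression.
3. Report two counts beside the table: patients in the CA-125 population below 2 x ULN, and qualifying ovarian patients in the Safety population with no posttreatment CA-125. The second count lets a reader judge the loss that the set definition causes in the other direction.

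As a side note, name the population for the irRC and IWG best-response tables, so that the unevaluable and Missing categories agree with sets that require a posttreatment assessment.

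The cost is SAP wording, one baseline flag and two counts, with no new data. The downsides are two denominators in one table, which need clear labels, and a smaller denominator for response.
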